11.4.3 Analyses for secondary outcomes

Behavioral secondary outcomes will be treated statistically the same way as the primary outcome, but a Bonferroni correction (i.e. corrected for the number of behavioral secondary outcomes) will apply separately for the main effect (i.e. drug vs. placebo) and the interaction effect (i.e. main effect x acute vs. repeated administration). In the case of a significant (i.e. Bonferroni-corrected) interaction effect, post-hoc analysis will be applied to describe the interaction effect.

The measure of the non-behavioral secondary outcome (i.e. rMT) will be treated statistically the same way as the primary outcome measure.

11.4.4 *Interim analyses*

No interim analyses are planned.

11.4.5 *Safety analysis*

Safety data will be analyzed for all participants, who received at least one dose of study medication.

11.4.6 *Deviation(s) from the original statistical plan*

Deviations from the original statistical plan will be justified and reported to the ethical committee and regulatory authorities.

Deviation from the original statistical plan will be performed, if reviewers demand specific analyses. If in the meantime other studies find important effects or confounding effects related to our study, we will include these found confounders (if we have assessed those) as an additional analysis in our statistical plan beside our planned analyses.

11.4.7 *Handling of missing data and drop-outs*

Missing data will be recorded as NA.

Drop-Outs see chapter 11.4.1.

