11.2 Determination of Sample Size

We are interested to detect a drug effect with at least medium effect size. The estimation of N=44 is based on a power analysis using dependent two-tailed t-tests assuming to detect a medium effect size (Cohens $dz = 0.5$) with a power of 90% at $\alpha=0.05$ (software: G-power 3).

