11.4 Planned Analyses

All analyses will be performed with the software R. The differences between the experimental conditions (placebo, verum) will be analyzed using linear mixed models in combination with analysis of variance (SS II). Subjects will be included as the random effect of the mixed model. Sex and age will be inserted as covariates.

In case of significant interactions between covariates and experimental condition, post-hoc tests will be applied to describe the interaction.

To control for an influence of other variables, possible confounders will be entered into the model as covariate (each possible confounder entering the statistical analyses separately and corrected for multiple comparisons with the Bonferroni method).

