11.4.2 Analysis for the primary outcome

A significance level of $p < 0.05$ will be considered as significant.

The dependent variable is the primary outcome (i.e. 3-back (d')) after repeated administration of study medication). The independent variable of interest is the experimental condition (placebo or verum).

To control for possible confounders or moderators, we will also consider tiredness, motivation, headache, gastrointestinal discomfort, dizziness, mood as assessed by MADRS-S, potassium blood concentration at screening, body weight, duration of washout period and vital signs as covariates (each covariate entering the statistical analysis separately). In case of a significant (i.e. after Bonferroni correction for multiple comparisons) interaction between independent variables of interest and covariates, post-hoc analysis will be applied to describe the interaction effect.

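### Holm's step-down procedure would give the behavioural secondary outcomes the same family-wise error control as the planned Bonferroni correction, with equal or higher power

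*Combined protocol and SAP*

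**What the plan says.** Section 11.4.3 plans a Bonferroni correction for these outcomes, "corrected for the number of behavioral secondary outcomes", applied on its own to the main effect of drug versus placebo. It treats as a second family "the interaction effect (i.e. main effect x acute vs. repeated administration". A significant corrected interaction leads to post-hoc description. No stepwise method is mentioned.

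The resting motor threshold lies outside both families: "The measure of the non-behavioral secondary outcome (i.e. rMT) will be treated statistically the same way as the primary outcome measure". Section 11.4.2 sets 0.05 for the primary outcome.

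The family size is not given as a number. Section 5.2 has six behavioural bullets: acute 3-back d', 3-back reaction time, 0-back, SDMT, BOMAT and digit span. The last covers forward and backward scores, so the count is six or seven. All except acute 3-back d' are measured after both acute and repeated intake.

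Section 11.2 bases N = 44 on a "power analysis using dependent two-tailed t-tests" with dz = 0.5, 90% power and alpha 0.05. That calculation covers one comparison at the unadjusted level.

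**The concern.** Single-step Bonferroni holds every outcome in a family to 0.05/m, however many of the others have already been rejected. Holm starts at the same 0.05/m and relaxes the threshold after each rejection. It uses the same p-values and needs no assumption about how the cognitive scores correlate, which suits several scores taken from the same participants.

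What is at stake is power for the secondary outcomes. Section 4.3 names several domains (working memory functions, attention, processing speed, fluid intelligence). If the drug affects more than one of them, the planned rule will miss some effects that an equally strict rule would find.

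**Working it through.** **Plan's own figure.** For a two-sided paired t-test, df = n − 1 and noncentrality = dz × √n. At n = 44 the noncentrality is 0.5 × √44 = 3.317, and exact power at alpha 0.05 is 90.0%. At n = 43 it is 89.3%. N = 44 reproduces.

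**Bonferroni at N = 44, dz = 0.5, one paired comparison per outcome.**
- m = 7: 0.05/7 = 0.00714, power 68.7%.
- m = 6: 0.05/6 = 0.00833, power 70.7%.

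Section 11.2 gives dz = 0.5 for the sample size only. Applying it to the secondary outcomes is an assumption made here.

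**Holm's rule.** Order the p-values from smallest to largest. Compare the j-th with 0.05/(m − j + 1) and stop at the first failure. For m = 7 the thresholds are 0.0071, 0.0083, 0.0100, 0.0125, 0.0167, 0.0250 and 0.0500. Bonferroni uses 0.0071 throughout. Every p-value at or below 0.05/m passes its Holm threshold too, so Holm rejects all that Bonferroni rejects.

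**Error control.** Suppose m0 null hypotheses are true. The first true null to be rejected must be reached by step m − m0 + 1 at the latest, so its p-value is at most 0.05/m0. The chance that any of the m0 p-values is that small is at most m0 × 0.05/m0 = 0.05, whatever the correlation.

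**Size of the gain.** Simulated paired t-tests, n = 44, dz = 0.5 for each true effect, at least 20,000 trials per scenario, equal correlation between outcomes of 0 or 0.3 (assumed, as the documents give none). Average power per true effect:

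| m | True effects | Bonferroni | Holm (range over correlation 0.3 to 0) |
|---|---|---|---|
| 7 | 1 | 69% | 69% |
| 7 | 3 | 69% | 71–72% |
| 7 | 5 | 69% | 75–76% |
| 7 | 7 | 69% | 81–83% |
| 6 | 1 | 71% | 71% |
| 6 | 3 | 71% | 74% |
| 6 | 6 | 71% | 83–84% |

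No simulated trial had a Bonferroni rejection that Holm missed. With all nulls true the two methods have the same family-wise error (m = 7: 4.9% at correlation 0, 4.6% at 0.3). In mixed scenarios Holm's was at most 5.0%.

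**Smaller effects.** At dz = 0.3 with three true effects out of seven and correlation 0.3, average power goes from 22% to 23%.

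**Main effects over two occasions.** Most behavioural outcomes give two drug–placebo differences per person. If each has dz = 0.5 and the two correlate r, their mean has dz = 0.5/√((1 + r)/2):
- r = 0.5: dz = 0.577, Bonferroni power at 0.05/7 is 83.6%.
- r = 0.8: dz = 0.527, power 74.5%.
- r = 1: dz = 0.5, power 68.7%.

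These values of r are assumptions. The table therefore describes the single-comparison case. The interaction family was not simulated: Holm's ordering over Bonferroni holds there too, but the size of the gain is not computed.

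**The case against.** The strongest reply is that nothing here is wrong. Bonferroni is pre-specified and controls error within each family, and the choice between two valid methods is a preference. That stands, and it limits the point to an optional improvement.

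The gain also depends on the pattern of effects. It is nil if one outcome responds and about 3 points if three do at dz = 0.5. It reaches double figures only when all outcomes respond. Holm does not make the first rejection easier: with all seven effects true, the chance of at least one finding is the same under both methods. This also stands.

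A reader might infer that the trial promises 90% power for its secondary outcomes and delivers 69%. The documents do not support that. Section 11.2 makes no power claim for secondary outcomes, and the 69% rests on a single-occasion test, while most planned main effects can use acute and repeated data.

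A reader might also carry the change over to the confounder tests in 11.4, which are "corrected for multiple comparisons with the Bonferroni method", and to those in 11.4.2. No gain has been worked out for them, and their number is not fixed (vital signs, for example, are not itemised), so they are left out.

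The change is not wholly without cost either. Bonferroni has simple matching simultaneous confidence intervals and Holm does not, although the plan asks for none.

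**Conclusion.** The point holds as an efficiency gain. Within each family Holm gives the same 5% family-wise error under any correlation and is never less powerful. That conclusion does not depend on the family size, the effect size or the planned mixed model, provided that each test yields a valid p-value.

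The size does depend on assumptions. With N = 44, one paired comparison per outcome, dz = 0.5 for each true effect and correlations of 0 to 0.3, the gain in average power is nil with one true effect and about 3 points with three, for either family size. It is about 12 to 15 points when every outcome responds. It is about 1 point with three true effects at dz = 0.3, and would differ for main effects that pool acute and repeated data.

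It would be wrong to conclude that the planned correction is invalid or that the secondary results could not be trusted. The primary test, its 0.05 level and N = 44 are unaffected. Holm also leaves the two-family structure and the separate test of resting motor threshold as they are.

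**What to change.** Before unblinding, replace the Bonferroni correction in 11.4.3 with a Bonferroni-Holm step-down correction, applied within the same two families (drug main effects; drug-by-acute/repeated interactions). Listing the tests in each family in the same edit would settle whether the count is six or seven, which either method needs. It would also settle whether acute 3-back d', measured as a secondary outcome on one type of occasion only, belongs in the interaction family.

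Cost: a wording change and one argument to the p-value adjustment function in R, the software named in 11.4. No change to N, visits or the primary analysis. Matching simultaneous confidence intervals become less simple. The change must be documented and, under 11.4.6, justified and reported to the ethics committee and the authorities. It should be dated before anyone sees results by treatment, because choosing Holm after seeing the p-values would not be credible.

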5.2 Secondary Outcomes

- High-load working memory performance (3-back (d')) as assessed by a letter n-back task) after acute intake of study medication (visit 2 and 4)
- rMT measurement using TMS after repeated intake of study medication (visit 3 and 5)

Performance in other working memory-related tasks and other n-back outcomes after acute and repeated intake of study medication

- Reaction time (for correct 3-back responses)
- Performance in a 0 back task as a measure of attention
- Symbol Digit Modalities Test, SDMT (Smith 2013, 13th edition)
- BOMAT - advanced (Hossiep/Turck/Hasella, 1999)
- Digit span forward and backward performance (von Aster 2006)

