6 STUDY DESIGN

6.1 General study design and justification of design

Pharmacological proof-of-concept study on the effects of 10 mg fampridine (twice daily oral administration) on physiological processes, in particular working memory, in healthy participants using the following design:

- randomized
- double-blind (participant, study team)
- placebo-controlled
- cross-over
- counter-balanced

The duration of the study from first participant in to last participant out is approx. 24 months. Duration for an individual study participant will be at most 7 to max. 15 weeks, depending on the duration of the wash out period.

There will be two intervention periods of 3.5 days during which medication (fampridine /placebo) will be applied separated by a wash out period of 8 (days between Visit 3 and Visit 4; equivaling over 30 half-lives of the study drug) up to 82 days (12 weeks).

Two test days will take place during each intervention period: one on the first day and one on the last day of each period during which cognitive functions under the influence of fampridine/placebo will be assessed using parallel versions of tests.

At the beginning of test day 1 (visit 2), each subject will be randomized to receive either placebo or fampridine first.

After the administration of study medication (visits 2-5) there will be a 4-h waiting period allowing the medication to reach peak cerebrospinal fluid levels (Hayes 2004). After this time period, the cognitive test battery will be administered.

At the end of each visit, participants will be asked about their actual wellbeing. If there are no complaints or symptoms, participants can be dismissed. In case of minor health problems, the participant will have to stay in the study center until recovery under medical supervision. In case of more severe incidents staff acts according to chapter 10.4.6.

The study will end for the subjects in the evening of the second test day of the second intervention period (visit 5). The duration for the different study parts see table 1 (Duration of Study parts, page 12).

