8 STUDY INTERVENTION

8.1 Identity of Investigational Products

8.1.1 Experimental Intervention

Active study medication consists of 7 tablets of fampridine 10 mg formulated for oral administration taken in the morning and evening 12 h apart without food. Tablets must be administered whole: do not divide, crush, chew, or dissolve Fampyra® retard tablets.

There will be a washout period of at least 8 days equaling over 30 half-lives of the active substance fampridine ($t_{1/2} = 6$ h) between experimental and control intervention and up to 82 days (12 weeks) depending on the individual scheduling of each subject.

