11.4.1 Datasets to be analyzed, analysis populations

We will apply a Per-Protocol-Analysis, i.e. the analysis of the primary and secondary outcome measures will be only performed with those participants, who completed all tests and investigations. There will be replacement of Drop-Outs until data of 44 participants are completed. Drop-Outs will be thoroughly described to assess the reason(s) for dropping out.

We will recruit up to 4 subjects more towards the end of the trial to prevent under-recruitment due to Drop-Outs. If more than 44 subjects will complete all tests and investigations their data will also be analyzed.

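### For secondary outcomes scored at four visits, a subject-only random effect and no period term put drug and drug-by-time on one pooled error, so neither test is assured its Bonferroni level

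*Combined protocol and SAP*

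**What the plan says.** Section 11.4 sets a linear mixed model with type II analysis of variance: "Subjects will be included as the random effect of the mixed model". On fixed terms it adds "Sex and age will be inserted as covariates". Section 11.4.2 lists further covariates, entered one at a time, ending with "duration of washout period and vital signs as covariates". Neither list has period, visit or sequence. Washout duration is one value per person, so it cannot stand in for a period term.

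Section 11.4.3 treats the behavioral secondary outcomes like the primary, but tests two effects on them, each Bonferroni-corrected: "the main effect (i.e. drug vs. placebo) and the interaction effect (i.e. main effect x acute vs. repeated administration". A significant interaction leads to post-hoc description. No model formula is given.

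The layout comes from two other places. Section 5.2 lists "Performance in other working memory-related tasks and other n-back outcomes after acute and repeated intake of study medication", and Section 6.1 states: "Two test days will take place during each intervention period: one on the first day and one on the last day of each period". Each of these outcomes therefore has four scores per person. Section 8.1.1 allows a washout of at least 8 days and "up to 82 days (12 weeks) depending on the individual scheduling of each subject". Section 9.2.2 uses parallel test versions across the test days. Section 11.4.1 says the efficacy analysis "will be only performed with those participants, who completed all tests and investigations".

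**The concern.** The primary outcome has one score per condition, so a random intercept for subject is enough there. Carried over to four scores, the same model mixes three sources of within-person variation into one error term. Drug changes only between periods, so its proper error is the between-period variation. The drug-by-time effect has its own, smaller error.

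The design gives reason to doubt that these errors are equal. The two test days within a period are days 1 and 4, while the periods are 8 to 82 days apart, so scores from one period may resemble each other more. Four parallel versions taken in succession invite practice or version shifts.

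At stake are the Bonferroni level claimed for the drug effect on five measures, and the power of the interaction test that decides whether the acute and repeated time points are examined separately.

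**Working it through.** **Plan's own figure.** A paired two-tailed t-test with dz = 0.5 at alpha 0.05 has power 0.8931 at n=43 and 0.9000 at n=44. The N=44 of Section 11.2 is reproduced and is not in question.

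**Inputs from the documents.** n=44; 2 periods × 2 test days; subject as the only random effect; no period term; complete cases. The number of behavioral secondaries is not stated: five to seven gives per-test levels of 0.0100, 0.0083 or 0.0071.

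**Assumed inputs.** With residual variance set to 1, a is the subject-by-period variance, b the subject-by-time variance, and s the period shift in residual SDs. The documents give none of these.

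**Error terms, equal sequences.** Fixed effects are drug, time and drug × time. The per-person contrasts are scaled so that residual variance contributes 1.

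- Proper error for drug: 1 + 2a
- Proper error for drug × time: 1
- Pooled error that the plan uses for both: 1 + (2/3)(a + b) + s²/3, on 4×44 − 44 − 3 = 129 df

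The drug test is above nominal when 1 + 2a exceeds the pooled error, which reduces to a > b/2 + s²/4. It is below nominal when a is less than that.

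**Approximate level.** 2Φ(−1.979 × √(pooled error / proper error)), where 1.979 is the 5% critical t on 129 df.

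- a=0.25, b=s=0: pooled 1.167. Drug: 1.979 × √(1.167/1.5) = 1.745, level 8.1%. Interaction: 1.979 × √1.167 = 2.138, level 3.3%.
- a=0.25, b=0.5, s=1: pooled 1 + 0.5 + 0.333 = 1.833. Drug: 1.979 × √(1.833/1.5) = 2.188, level 2.9%. Interaction: 1.979 × √1.833 = 2.680, level 0.7%.

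**Simulated levels at nominal 5%, 22 per sequence:**

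| a | b | s | Drug | Drug × time |
|---|---|---|---|---|
| 0 | 0 | 0 | 5.1% | 5.0% |
| 0.25 | 0 | 0 | 8.2% | 3.6% |
| 0.5 | 0 | 0 | 10.8% | 2.5% |
| 0.25 | 0.25 | 0.5 | 5.6% | 2.0% |
| 0.25 | 0.5 | 1 | 3.1% | 0.8% |

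At the Bonferroni levels, a=0.5 with b=s=0 gives drug/interaction levels of 3.49/0.32% (nominal 1%), 3.06/0.25% (0.83%) and 2.74/0.20% (0.71%).

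**Unequal sequences.** The rule above needs equal numbers. With 26/18 completers and no period term, the drug estimate is biased by s × (26 − 18)/44 = 0.18s. With a=b=0 and s=1, the simulated drug level is about 2.3% at 22/22, 5.0% at 24/20 and 14% at 26/18.

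**When the interaction test exceeds its level.** Suppose individual acute and repeated drug responses each have variance 1 and correlate at −0.5. The drug, time and interaction errors are then 1.25, 1.75 and 1.75, the pooled error is 4.75/3 = 1.58, and the interaction level is 1.04% against 0.71%. A period × time shift of 1 SD at 26/18 gives about 7% at nominal 5%.

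**Interaction power.** Take a true interaction of 0.87 residual SD, which the contrast test proposed below detects with 80% power at 5%. Under the plan's model, power is 81% with no clustering, 77% at a=0.25 alone, 69% at (a, b, s) = (0.25, 0.25, 0.5) and 64% at (0.25, 0.5, 0.5).

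**The case against.** The strongest reply is that the plan is brief rather than wrong: it gives no formula and does not forbid further random terms, so the analyst could add them. That stands in part. But Section 11.4 names subject as the random effect in the singular, and Section 11.4.3 says to proceed as for the primary outcome. A reader following the text fits the pooled-error model.

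Second, with no variance components in the documents, nobody can show that this trial's tests are materially off, and several settings lie near nominal. This is correct. It also rules out two stronger readings. A reader might infer that the drug test is inflated; with equal sequences that holds only when a > b/2 + s²/4, and other settings push the level down. A reader might infer that the interaction test is always conservative; it is at nominal level when all components are zero, and it can exceed nominal in the two situations shown above.

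Third, a large sequence imbalance may not occur. Section 6.2.1 limits imbalance at allocation. However, it replaces drop-outs only after all kits are assigned and aims for approximately 44 completers. Section 11.4.1 analyses completers only, including up to four extra participants. Unequal completers are therefore possible, and 26/18 is an illustration rather than a forecast.

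**Conclusion.** The point holds for the five secondary measures scored at four visits. As written, the drug and drug-by-time tests share an error that is right only if subject-by-period variance, subject-by-time variance and period shift are all zero. Otherwise neither test is assured its stated Bonferroni level. For the drug test the direction is unknown. For the interaction test the usual result is lost power.

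The sizes (drug level about 3% to 8% at nominal 5% in the two equal-sequence examples, about 14% at 26/18 with a 1 SD shift) rest on assumed variance components and shifts. The existence of the problem does not depend on their exact values.

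A reader might also infer that the main result is undermined. The documents do not support that. The primary outcome and rMT, and acute 3-back analysed on visits 2 and 4 alone, have one score per condition and no pooled-error problem, and N=44 is unaffected. This is a correction that should be made, limited to secondary outcomes.

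**What to change.** In Section 11.4.3, for each four-visit outcome, compute two values per person:

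1. the fampridine-minus-placebo difference in period means (drug effect);
2. the fampridine-minus-placebo difference in acute-to-repeated change (drug × time).

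Test each with adjustment for sequence/period, on its own error (44 − 2 = 42 df). In simulation these tests stayed between 4.8% and 5.2% at nominal 5% in every equal-sequence setting. Drug-by-sex and drug-by-age can be tested by adding sex or age to the first regression; covariates that change by visit enter as the matching differences.

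The alternative is a mixed model with fixed condition × time and period (plus period × time if sequences are unequal) and random subject, subject-by-period and subject-by-time terms. Adding subject-by-period alone does not restore the interaction test (1.9% at nominal 5% for a=0.25, b=0.5). With all three random terms, some variance was estimated as zero in 1% to 67% of simulated fits, and levels ran from 4.3% to 5.1% for drug and 4.9% to 6.3% for interaction.

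Costs:

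- No new data, but a text amendment. It may fall mid-trial: the synopsis plans the first participant for 09/2021 and dates this version 05/04/2022. Section 11.4.6 requires the change to be justified and reported.
- If there is no clustering, drug intervals widen by 2.0% at the 5% level (critical t 2.018 against 1.979) and 3.2% at the 1% level (2.698 against 2.614). Interaction power falls from 81% to 80%, or from 83% to 80%, respectively.
- Sections 11.4.7 and 12.3.3 allow a completer's single score to be NA or filtered out. The contrasts would then lose that person for that outcome, whereas the mixed model keeps the remaining scores.
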